## Suubi4Her Proposal

Final Version: 7-September-2017

**Study Overview.** The Suubi4Her program will test the effects of a combination asset-based financial inclusion intervention (YDAs) with an evidence-based family strengthening intervention to be delivered via multiple family groups (MFG) to understand the effects and costs associated with a combined intervention versus YDA alone. Specifically, the proposed study addresses three study aims:

**Aim 1.** Examine whether the *Suubi4Her* intervention is effective in protecting adolescent girls against known HIV risk factors (including economically-motivated sex and intimate partner violence).

**Aim 2.** Elucidate the effects of the *Suubi4Her* intervention on behavioral health functioning (i.e., depression, self-efficacy and hopelessness) and examine the effects of these variables as potential mechanisms of change, mediating the relationship between each intervention and HIV risk reduction.

**Aim 3.** Evaluate the cost-effectiveness of each intervention condition.

To address the three aims guiding the proposed study, we will randomize girls (at the school level) to one of three study conditions: 1) YDA condition with a 1:1 saving incentive match rate – for educational purposes and microenterprise development (n=420 participants; n=14 schools); 2) YDA + MFG intervention condition (n=420 participants; n=14 schools); 3) A control condition receiving standard health and sex education provided in schools (n=420 participants; n=14 schools). We detail the three study arms below.

**Matched Savings Accounts (YDA) Intervention.** The Suubi4Her matched savings account will be in the form of a Youth Development Account (YDA), where savings are housed at a local bank and deposits made by the adolescent and family are matched, up to a match cap, by the intervention to encourage savings. Each adolescent assigned to a YDA group will receive a YDA held in her own name in a financial institution registered by the Central Bank (Bank of Uganda). We have partnered with Centenary Rural Development Bank and DTB Bank to host the YDAs. Any of the adolescent's family members, relatives, or friends will be allowed and encouraged to contribute towards the YDA. The account will then be matched with money from the study. The maximum family contribution to be matched by the program will be an equivalent of US\$10 per month (in Uganda shillings) per family or US\$240 for the 24-month intervention period. Girls who save the maximum amount will have a total of \$480 at the end of the intervention (\$240 in savings plus \$240 from the match: a 1:1 match).

Each month, a bank account statement will be generated for every girl to note her accumulated savings. Also, during the intervention period, each girl, with her primary caregiver as a co-signer, will have access to the money in her account (excluding the matching funds). This option is provided in case of an emergency (for example, a family illness). Participants can withdraw their own money—but not the matching funds. When the girls turn 18, they will no longer need co-signers. The matching funds will be kept in a separate account from the participants' own savings. When a girl is ready to pay for school fees, the check for the matching funds will be written in the name of the school she attends. Alternatively, the matching funds may be wire transferred directly to the school's bank account. The student will then contribute her portion of the total cost for the academic term out of her savings account—for which she will be a signatory. The same will apply to girls who want to invest a portion in small business development: the check will be written to the vendor for the wire transfer for the match will be

[figure not shown]
sent directly to the vendor with the required particulars of the participant). The accounts will be monitored by Drs. [name] (PI) and [name] (in-country Co-I), assisted by the project coordinator and financial manager in Uganda. Experience with our earlier studies indicates the accounts are easy to monitor through monthly bank statements. A participant's access to the matching funds is conditional upon completion of 12 financial management workshops over 12 months.

The matched savings accounts include financial management (FM) workshops and an IGA promotion component. The FM workshops, to be implemented by our collaborating community agency (RTY-Uganda) in collaboration with the financial institutions holding the YDAs, will consist of 12 general workshops that will: a) introduce participants to the notion of asset-building; b) cover asset-building strategies in detail, e.g., saving and investing in IGAs; c) cover specific topics related to saving, e.g., the importance of saving and how it can be done. There will also be asset-specific trainings following the general FM workshops.

**Combination Intervention: Youth Development Accounts (YDA) + Multiple Family Groups (MFG).** This arm is intended to directly address both the economic needs of the participating adolescent girls as well as their mental health functioning. This combination arm tests whether combining two evidence-based interventions will reduce HIV risk over and above a financial intervention (YDA) or usual care alone. The combined arm will consist of: a) a family monetary savings program using Youth Development Accounts (YDA) (detailed above), and b) a family-based dialogue and training via Multiple Family Groups (MFGs) focused on strengthening family relationships and mental health challenges which frequently accompany adolescent girls' transition to adulthood.

Girls in the combination intervention group (YDA + MFG) will receive: 1) a monetary savings account in the form of a YDA, matched at a rate of 1:1. The YDA will operate exactly the same way as in a YDA-only group—detailed above; 2) in addition to the YDA, each girl will also be invited, together with her caregiving family, to attend 18 60-minute MFG sessions, over the course of 18 months, to be hosted within the community. The 18 sessions include an introductory session and a program evaluation session. Each session will involve 6-12 families. The MFG curriculum will incorporate broad conceptual categories targeting family-level issues and concerns that may impact families' abilities to incorporate new behaviors. Each session will provide numerous opportunities for family members to discuss the realities of family life, as well as perspectives on culture and values, specifically those related to gender. Content is intended to foster both within and between family interaction, learning and communication. Sessions will be facilitated by trained community-level Lay Counselors composed of priests, village health care workers and community extension workers. Training of Lay counselors and having them facilitate the MFG is intended to ensure intervention fidelity, and build capacity to sustain the intervention for the community at study end.

**Usual Care: Health and Sex Education and HIV Prevention Curriculum in Secondary Schools.** Two curriculums will be delivered in all our participating secondary schools: Life Planning Skills and Adolescent Sexual Reproductive Health. All enrolled participants, both in control and treatment conditions, will be exposed to these curriculums. Specifically, the content related to HIV and sexual risk-taking behaviors will include delaying sex; using condoms and contraception; preventing forced sex; and preventing substance abuse. This curriculum will also include education on gender equality. The content will primarily be delivered via lecture. Generally, Adolescent Sexual Reproductive Health content is and will be dispersed across a range of academic subjects in secondary schools. In each class, students tend to receive information about sexual activity, HIV prevention, and gender relevant topics. Prior to study

implementation, we will hold induction meetings for all teachers involved in the study to ensure uniform delivery of this bolstered usual care.

[figure not shown]
### Study Significance

Adolescence is a particularly vulnerable stage of development with high risk for HIV, STIs and poor mental health functioning. Adolescence is an intense period of development characterized by rapid physical, social and emotional maturation. It requires sufficient family and community support to successfully navigate (WHO, 2014). Financial stress experienced by economically insecure families in low-resource communities compromises the support available to adolescents as they transition to adulthood, putting them at increased risk of experimenting with unhealthy behaviors (McLoyd, 1998; WHO, 2014). Adolescents facing adversity, particularly poverty, exhibit high rates of early and risky sexual behavior, pregnancy, and drug abuse (Ministry of Health Uganda and ORC Macro, 2006; WHO, 2014). Simultaneously, although less researched in high poverty global contexts, adolescents face serious challenges to mental health functioning with trends varying by age and gender. Beginning in adolescence, females suffer more from internalizing disorders, including depression and anxiety and also endure more self-blame, hopelessness, and low self-esteem (Rosenfield & Mouzon, 2013; Thapar, Collishaw, Pine, & Thapar, 2012). Moreover, adolescents affected by AIDS experience even more severe mental health problems than other at-risk groups (Cluver, Gardner, & Operario, 2008; Han, [name], & Wang, 2013). Indeed, previous studies of AIDS-affected Ugandan adolescents living in poverty show high rates of depression (Han et al., 2013; [name], Neilands, Waldfogel, & Ismayilova, 2012) anxiety, learning problems, (Curley, [name], & Han, 2010; [name] & Curley, 2006) and risky sexual behaviors. ([name], Ismayilova, et al., 2010; [name], Keun, Neilands, Ismayilova, & Sperber, 2010). Compounded by poverty, the devaluation of self and lack of hope for the future can influence decisions on sexual risk taking and increase HIV risk. Yet, most research on children and families in AIDS-impacted communities in Sub-Saharan Africa (SSA) has primarily focused on meeting the psychosocial needs of younger children, (Jennings, [name], & Nabunya, 2016; [name] & Curley, 2006; [name], Karimli, Chang-Keun, & Ismayilova, 2010) failing to consider that addressing families' access to economic resources and strengthening capacity to respond to adolescent mental health may be critical to reducing HIV risk.

SSA remains the world's most affected region in the HIV epidemic (UNAIDS, 2014) with girls accounting for 7 out of 10 new infections among adolescents (ages 15-19 years) (UNICEF, 2016). This gender disparity has increased recognition that adolescent girls need more attention in the fight against HIV/AIDS in the region.

Given the complex and multi-dimensional reasons for increased HIV risk among adolescent girls in SSA, and the failure of most single interventions to significantly decrease these rates, UNAIDS and others in the HIV research community have observed an urgent need for strategies to shift towards Combination HIV Prevention (CHP) (Hankins & de Zalduondo, 2010; UNAIDS, 2010). This is the reason for the proposed *Suubi4Her* study aimed at testing the impact of a combination family-based economic empowerment through Youth Development Accounts (YDAs) with an evidence-based family strengthening intervention delivered via multiple family groups (MFG). The study design will allow us to examine and understand the effects and costs associated with each of these interventions individually, and in combination.

The proposed *Suubi4Her* study uses a combination intervention to address multiple layers of girls' transitions both on the individual and familial levels. Specifically, the *Suubi4Her* study will examine questions regarding impact using both objective and subjective measures, scale-up, and cost of the intervention for an older age group and the extent to which a combination intervention will protect older girls against known HIV risk factors and enhance several

outcomes: financial stability (asset-accumulation), educational achievement (school enrollment, attendance, and attainment), sexual risk-taking behavior, and mental health functioning.

In summary, the proposed study innovates by testing an innovative combination intervention that has a potential to promote sustainable behavioral change among older adolescent girls by use asset-development incentives (savings match) and behavioral economics principals.

**Design and Methods.** The proposed study examines the effectiveness of: 1) the combined YDA+MFG vs. YDA-alone; 2) YDA + MFG vs. Usual Care; and 3) YDA vs. Usual Care, and determine key factors influencing scale up via a three cluster randomized control trial (RCT). The three groups include: 1) YDA condition with a 1:1 saving incentive match rate; 2) Combined YDA+MFG intervention condition; 3) Usual Care alone.

**Assessments.** We will have four assessment points: baseline (pre-test), 12, 24, and 36-months post-intervention initiation. All Assessments will take place at the child's home with each lasting about 60 minutes. Although all the children will be attending school, and we expect all of them to be English-speaking (the instructional language in all Ugandan schools), assessments will be conducted in English or Luganda (local language) depending on participants' English proficiency. All interviewers will be fluent in English and Luganda. Questions will be translated from English to Luganda and back-translated by a certified translator from a local University (Department of Languages) following standard procedures. Drs. [name] and [name] (fluent in Luganda and English) will cross-check all translated assessments. All interviewers will receive a highly structured and intensive training conducted by Drs. [name] and [name]. All measures used have been or will be pre-tested and made culturally appropriate to the Ugandan context. For questions measuring sensitive behaviors (i.e., sexual risks), we will use Audio Computer-Assisted Self-Interviews (ACASI) where the participant takes the survey herself on a mini laptop. Non-sensitive questions will be interviewer-administered.

**Study Population.** A total of 1260 secondary school-going girls (ages 15-17 at enrollment) in their first year of secondary school will be enrolled and followed for the 12 academic terms (through the last year of lower secondary school—Senior 4). To avoid stigma that surrounds being HIV positive in the region, no girl will be excluded by virtue of their HIV status. Rather, girls who test HIV positive during the baseline interviews will be referred for care and support (in the event they are not already in care) to our extensive network of collaborating clinics and NGOs in the study area, depending on the girl's preference. Once a girl has been linked to care, we will follow-up within thirty days to ensure she has been enrolled. We will also verify whether the referred girls are engaged in care during our follow-up interviews. Similarly, girls testing positive for pregnancy will be linked to antenatal care services at an existing health facility of their choice, and will thereafter be followed up by peer mothers for peer support while those testing positive on STIs (Gonorrhea, Trichomonas and Chlamydia) will be linked to STI treatment clinics offering adolescent-friendly services, or to the Rakai Health Sciences Program STD clinic, whichever the participant prefers. Girls will not be excluded for pregnancy status nor STI/STD status.

#### **Selection of Participants**

The target population for this study are older adolescent girls (ages 15-17 at enrollment), in secondary school and living within the four districts of Uganda: Masaka, Rakai, Lwengo and Kalungu. HIV prevalence in this region is 9.8%, compared to other regions in Uganda (7.3%).

**Inclusion Criteria:** Specifically, for an adolescent to be included in the study, she will have to meet the following criteria: (1) female; (2) enrolled in her first year of secondary school (senior

1) in Rakai, Masaka, Lwengo or Kalungu districts; (3) age 15-17 years; (4) living within a family (broadly defined and not an institution or orphanage, as those in institutions have different familial needs).

**Exclusion criteria:** Girls are ineligible if: (1) they have a cognitive or severe psychiatric impairment that would prevent comprehension of study procedures as assessed during the Informed Consent process (see Recruitment and Consent Section) or; (2) they are unwilling or unable to commit to completing the study.

We will not exclude girls because of their HIV, STI and/or pregnancy status and the analysis will be adjusted to account for these baseline factors. Girls testing positive for HIV, STI (Gonorrhea, Trichomonas, or Chlamydia) or pregnancy will be referred for care and support (see *Study Population* above). A plethora of services, including access to free antiretroviral therapy (ART), and counseling exist for children and adults living with HIV in the study region. We will follow up with all girls who test positive for HIV or an STI within 30 days of referral, to check on their engagement in care. For girls who test HIV positive, engagement in care will be verified annually using clinical and viral load records.

Study participants will receive their HIV results independently, and then proceed to inform their parent or guardian, upon receipt of the child's consent to do so. Research Assistants will contact girls who test positive 30 days after disclosing their status, to confirm that they have connected with follow up care and have access to comprehensive care services. If not already attending a local clinic, girls will be referred for care to one of the 39 clinics (currently participating in the *Suubi+Adherence* study) with whom [name] (PI) and research team have established partnerships within the Greater Masaka Region. Girls testing positive for Gonorrhea, Trichomonas or Chlamydia will be linked to sexually transmitted infection treatment clinics offering adolescent-friendly services, or to the Rakai Health Sciences Program STD clinic, whichever the participant prefers. Girls who are pregnant at the time of enrollment will be linked to antenatal care services at an existing health facility of their choice (within the study area), and will thereafter be followed up by peer mothers for peer support. While *Suubi4Her* is primarily situated within a prevention framework, it will also seek to understand the intervention effects for girls who are HIV positive, adjusting analysis to account for these baseline factors.

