Our primary interest is to estimate the marginal or population-average effects of intervention participation on HIV risk outcomes rather than the effect for a hypothetical average subject or school. Moreover, within-subject and within-school HIV risk outcome correlations are considered nuisance parameters rather than quantities of interest to be modeled explicitly. Accordingly, generalized estimating equations (GEE) will be used to perform the proposed primary analyses to test Hypotheses H1A-H1C. These hypotheses will be tested by three pairwise planned time-averaged comparisons of post-baseline measurements. Alpha ( $\alpha$ ) will be set at  $.05/3=.017$  for these three planned comparisons to maintain a nominal  $\alpha=.05$ . Any additional post-hoc comparisons (e.g., paired comparisons of groups at each time point) will maintain nominal alpha of .05 through the use of simulation-based stepdown multiple comparison methods. The alternating logistic regression (ALR) approach implemented in SAS PROC GENMOD will be used to address the 3-level clustering of observations within participants and participants within schools. Though GEE estimates are consistent even if the correlation structure is misspecified, GEE's statistical efficiency improves as the working correlation structure more closely approximates the actual correlation structure; therefore, various correlation structures suitable for the study's design will be considered (e.g., exchangeable; nested-1). The QIC statistic will be used to select the final correlation structure. Randomization strata indicators will be included as covariates as required by the stratified randomized design to obtain unbiased inferences. Additional covariates (e.g., HIV serostatus) will be included if they improve QIC. Robust Huber-White "sandwich" standard errors will be used to obtain correct inferences even if the chosen correlation structure remains slightly misspecified. GEE case deletion diagnostics (e.g.,

DFBetas, Cook's *D*) will be used to investigate whether influential cases are present; if such cases are found, results will be reported with and without influential cases included.

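### Adjustment for baseline HIV, STI and pregnancy status is promised outright in the eligibility text but left to QIC in the analysis section, and no analysis is specified for the stated interest in HIV-positive girls

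*Combined protocol and SAP*

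**What the plan says.** **Eligibility text.** Under Selection of Participants, after the exclusion criteria: "We will not exclude girls because of their HIV, STI and/or pregnancy status and the analysis will be adjusted to account for these baseline factors". No condition is attached, and three factors are named. The last paragraph of that section adds, of the study, that "it will also seek to understand the intervention effects for girls who are HIV positive, adjusting analysis to account for these baseline factors".

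**Analysis text.** Under Data Analysis Plan and Statistical Procedures, the Aim 1 analyses use GEE to "estimate the marginal or population-average effects of intervention participation on HIV risk outcomes". Randomization strata indicators are always in the model. For anything else the rule is: "Additional covariates (e.g., HIV serostatus) will be included if they improve QIC". QIC is also the criterion for the working correlation. Baseline STI and pregnancy status are not named as covariates.

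On contrasts: "These hypotheses will be tested by three pairwise planned time-averaged comparisons of post-baseline measurements". Further comparisons are allowed: "Any additional post-hoc comparisons (e.g., paired comparisons of groups at each time point) will maintain nominal alpha of .05". The Aim 2 section carries the same approach to the mental health outcomes. No section gives an arm-by-HIV-status term, a stratified or subgroup analysis, or an expected number of HIV-positive girls.

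**The concern.** There are two separate problems, and the first is the more important.

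**Adjustment.** An analyst cannot follow both rules if QIC fails to improve. QIC is computed from the fitted outcome model, so under the analysis text the outcome data decide whether HIV status is in the primary model. The adjustment stated to readers of the eligibility section may be absent from the reported result, and the covariate set may differ from one outcome to the next. That is data-driven model selection inside a primary analysis, where a fixed choice was available at almost no cost.

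**HIV-positive girls.** The study states an interest in the intervention effect for these girls, and adjustment is the only means named. A covariate for HIV status changes the baseline odds but leaves a single arm effect for everyone. If nothing else is specified, the stated question has no planned estimate.

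**Working it through.** The plan gives no figure for covariate adjustment or for this subgroup. The surrounding figures reproduce: 3 x 420 = 1260 girls, and 0.05/3 = 0.0167, which rounds to the stated .017.

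**Step 1. The two adjustment rules side by side.**

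| | Selection of Participants | Aim 1 analyses |
|---|---|---|
| Factors named | HIV, STI, pregnancy | HIV serostatus, as an example |
| Condition | none | only if QIC improves |
| When settled | in advance | after the outcome models are fitted |

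If QIC improves for all three factors, the rules give the same model. If it fails to improve for any one, the first rule keeps that factor and the second drops it. The documents give no order of precedence.

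**Step 2. What covariate adjustment estimates.** Take arm (A) and HIV status (H) as 0/1.

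- Adjustment only: logit P = b0 + bA·A + bH·H. The arm odds ratio is exp(bA) whether H is 0 or 1.
- With interaction: logit P = b0 + bA·A + bH·H + bAH·A·H. The arm odds ratio is exp(bA) in HIV-negative girls and exp(bA + bAH) in HIV-positive girls.

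This follows from the form of the model and needs no assumed numbers.

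**Step 3. An illustration (all inputs assumed).** Two arms of 420; 25% risk in HIV-negative controls; odds ratio 1.5 for HIV status; true arm odds ratio 0.6 in HIV-negative and 1.0 in HIV-positive girls. Logistic models were fitted to expected counts, ignoring clustering.

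| Prevalence | Adjusted model, single OR | Interaction model, HIV-negative / HIV-positive | 95% factor, HIV-positive | Interaction power, alpha 0.05 |
|---|---|---|---|---|
| 2% | 0.608 | 0.60 / 1.00 | 7.6 | 7% |
| 5% | 0.621 | 0.60 / 1.00 | 3.6 | 11% |
| 9.8% | 0.641 | 0.60 / 1.00 | 2.5 | 17% |

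The factor is the amount by which the odds ratio is divided and multiplied to give the interval. The single odds ratio stays near the HIV-negative value because most girls are HIV-negative.

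**Step 4. Size and precision of the subgroup.** Selection of Participants gives a regional prevalence of 9.8%, with no figure for girls aged 15-17. If it applied: 0.098 x 420 = 41 per arm. At half that (assumption): 0.049 x 420 = 20.6, taken as 20.

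For two groups of size n at a common risk p, SE(log OR) = sqrt(2 / (n·p·(1-p))), and the factor is exp(1.96 x SE).

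| n per arm | p | SE | Factor |
|---|---|---|---|
| 41 | 0.20 | 0.552 | 2.95 |
| 41 | 0.10 | 0.736 | 4.23 |
| 20 | 0.20 | 0.791 | 4.71 |
| 20 | 0.10 | 1.054 | 7.89 |

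Step 3 gives 2.5 rather than 2.95 at 9.8% because its assumed risk for HIV-positive controls is higher: odds (0.25/0.75) x 1.5 = 0.5, a risk of 33%.

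The last row is only indicative. It expects 20 x 0.10 = 2 events per arm, and the chance of none in a given arm is 0.9^20, about 12%. The formula ignores school clustering and attrition, which widen intervals, and repeated measures, which narrow them.

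Steps 3 and 4 show how imprecise a subgroup estimate would be. They do not measure any error in the planned primary result.

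**The case against.** **The sentence on HIV-positive girls is narrative, not a model statement.** It sits in the participant section, outside Aims 1-3 and outside the hypotheses. Adjusting the analysis could mean an adjusted analysis within HIV-positive girls, and the allowance for further comparisons does not rule out subgroup contrasts. This stands in part. A reader might infer that the plan commits to a method that cannot answer its own question, and the documents do not go that far. What they support is narrower: on the plain reading, which matches the same section's wording about ordinary adjustment, the method gives a common effect; on any other reading, the analysis is unspecified.

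**The risk of misreporting is conjecture.** A reader might also infer that the pooled odds ratio would be presented as the effect in HIV-positive girls. No section says so, and the analysis text labels its target as population-average. That inference should not be made.

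**Randomization protects the comparison.** With or without these baseline covariates, the arm comparison remains valid. This stands, and it limits the adjustment conflict to pre-specification and consistency.

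**A subgroup estimate would be nearly uninformative.** Interaction power of 7% to 17% before clustering supports this, and with very few HIV-positive girls the model might not be estimable. That argues against any test-based claim and makes dropping the statement a reasonable alternative.

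**Conclusion.** The conflict over adjustment is real and rests on the text alone: one section promises adjustment for three baseline factors, and the other makes inclusion depend on a fit statistic from the outcome models. The two need to be reconciled before outcome data are examined.

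The gap for HIV-positive girls is real but secondary: an interest is stated, and no analysis that would estimate the effect in that subgroup is specified. If the regional 9.8% applied, about 41 girls per arm would be available, fewer if prevalence at ages 15-17 is lower. An odds ratio would carry a 95% factor of roughly 3 to 8 across the prevalences and risks assumed in Step 4, before clustering.

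It would be wrong to conclude that the tests of H1A-H1C are invalid; they are valid under either covariate rule. This is a low-severity point with a cheap remedy.

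**What to change.** 1. State in the Aim 1 analysis section that baseline HIV, STI and pregnancy status enter the primary GEE as pre-specified covariates, together with the strata indicators, regardless of QIC. Carry the same rule to Aim 2.
2. Restrict QIC to the choice of working correlation.
3. State how girls without a baseline result are handled, since Potential Risks allows a girl to decline a procedure.
4. For HIV-positive girls, choose one of two courses.
   - Add arm-by-HIV-status terms to the same school-clustered model. Report arm effects for HIV-positive and HIV-negative girls with confidence intervals and numbers per arm, labelled exploratory and with no test-based claim. If too few HIV-positive girls are enrolled for the model to be fitted, report counts and proportions only.
   - Or drop the statement about effects in HIV-positive girls from Selection of Participants.

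**Cost.** The baseline tests are already part of enrollment, so no new data are needed. The change is a few sentences of text and, under the first course, a few model terms. The subgroup result will be openly imprecise.
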